## ABSTRACT

**Introduction** Current guidelines recommend open gastrectomy with D2 lymph node dissection and adjuvant chemotherapy as the standard treatment for advanced gastric cancer. However, the prognosis is not satisfactory. Perioperative chemotherapy has been proposed to improve survival. Although still in debate, the efficacy of laparoscopic distal gastrectomy (LDG) in patients with advanced gastric cancer has been demonstrated in a few trials. Therefore, LDG after neoadjuvant chemotherapy can be a candidate for future standard treatment on advanced distal gastric cancer. We propose a randomised phase II trial to compare LDG and open distal gastrectomy (ODG) after neoadjuvant chemotherapy for advanced gastric cancer.

**Methods and analysis** To test the efficacy and safety, a randomised, open-label, single-centre, phase II trial was designed to evaluate the non-inferiority of LDG compared with ODG after neoadjuvant chemotherapy, with 3-year recurrence-free survival as the primary endpoint. The chosen critical value of a non-inferiority margin was an increase of <8%. The study started in 2015 and enrolled 96 patients according to a prior sample size calculation. Intention-to-treat and per-protocol approach will be used for efficacy analysis, and as-treated analysis will be applied for safety analysis. The survival curves will be constructed as time-to-event plots using the Kaplan-Meier method and compared using log-rank tests and Cox proportional hazards model. All statistical analyses will be conducted in standard statistical software with a significance level of 0.05.

**Ethics and dissemination** This study was approved by the Peking University Cancer Hospital Ethics Committee. The results will be submitted for publication in peer-reviewed journals.

**Trial registration number** NCT02404753; Pre-results.

## INTRODUCTION

Gastric cancer is one of the most common malignant tumours and the second leading cause of cancer death worldwide. Due to the difficulty of screening and early diagnosis, approximately 80% of patients with gastric

## Strengths and limitations of this study

- The proposed study is one of the few randomised trials to compare laparoscopic distal gastrectomy with open distal gastrectomy after neoadjuvant chemotherapy for distal advanced gastric cancer.
- This trial aims to evaluate the efficacy and safety using short-term and long-term endpoints.
- We designed this study to be sufficiently powered to identify non-inferiority in terms of 3-year recurrence-free survival, although it may be underpowered to detect non-difference on other outcomes.
- This is a phase II trial performed at a single medical centre; thus, if the non-inferiority of laparoscopic surgery is proven, a subsequent larger multicentre phase III verification clinical trial may be needed.

cancer in China are already at advanced stage (ie, tumour, node, metastases (TNM) stages II and III) at first hospital visit. The established treatment for advanced gastric cancer is open gastrectomy with D2 lymph node dissection, and postoperative adjuvant chemotherapy of S-1 for 1 year or combination therapy with capecitabine and oxaliplatin for 6 months. Although such a treatment regimen is effective, the prognosis of patients is not satisfactory, which calls for a more intensive chemotherapy. From theoretical perspectives, an intensified chemotherapy can be better tolerated and complied by patients if being administered before the surgery. By far, two large European phase III trials, the Medical Research Council Adjuvant Gastric Infusional Chemotherapy (MAGIC) trial, and the Fédération Nationale des Centres de Lutte contre le Cancer (FNCLCC) and the Fédération Francophone de Cancérologie Digestive (FFCD) 9703 study, have provided supportive evidence that preoperative (neoadjuvant) chemotherapy results in high compliance, as

well as other favourable factors such as high rate of R0 resection and tumour regression, which lead to a better prognosis.

Laparoscopic gastrectomy has been used as a superior alternative to open gastrectomy to treat early gastric cancer. Although still in debate, the application of laparoscopic surgery in advanced gastric cancer has drawn increasing attention over the years. The most recent meta-analysis published in 2016 concluded that laparoscopic gastrectomy for advanced gastric cancer appeared to be comparable with open gastrectomy in the number of lymph nodes achieved, overall survival and disease-free survival, but had advantages over open gastrectomy in terms of faster postoperative recovery. However, 25 out of the 26 studies included in this analysis are retrospective, and randomised trials on laparoscopic versus open gastrectomy for advanced gastric cancer are scarce. Thus, more research providing higher level of evidence is needed.

It is therefore worthwhile to compare the safety and efficacy of laparoscopic and open gastrectomy when combining with neoadjuvant chemotherapy. There have been a few randomised trials comparing laparoscopic with open gastrectomy, and multiple on comparing gastrectomy with gastrectomy+neoadjuvant chemotherapy for advanced gastric cancer, but very few on the comparison between laparoscopic gastrectomy+neoadjuvant chemotherapy and open gastrectomy+neoadjuvant chemotherapy. To our best knowledge, only one similar trial was proposed to be carried out from 2011 to 2014 in Japan, but results have yet to be published. A retrospective study recently conducted by our team suggested that laparoscopic gastrectomy after neoadjuvant chemotherapy had comparable safety and efficacy as open gastrectomy in perioperative period. In particular, laparoscopic distal gastrectomy after neoadjuvant chemotherapy did not increase operation time, blood loss, postoperative complications and length of stay in the hospital compared with open gastrectomy. Additionally, patients in laparoscopy group can benefit from the shortened length of incision and faster recovery of gastrointestinal functioning. However, no significant difference was found between the two groups in proximal and distal margin, and the number of resected lymph nodes.

The present study therefore aims to evaluate the safety and efficacy of laparoscopic gastrectomy after neoadjuvant chemotherapy for distal advanced gastric cancer using a randomised phase II clinical trial design, and to provide theoretical basis for conducting a multicentre phase III verification clinical trial.

## METHODS AND ANALYSIS

### Trial design

[figure not shown]
The current study is a prospective, randomised, open-label, single-centre, non-inferiority phase II clinical trial using a parallel-arm design. The study is designed on the hypothesis of non-inferiority on the basis of prior

study comparing laparoscopic and open gastrectomy for advanced gastric cancer. The study takes place in the Gastrointestinal Cancer Center of Peking University Cancer Hospital and Institute. Patient enrolment started on 23 April 2015, and the trial is expected to end in 2020. Figure 1 summarises the design of the trial, and each of the trial's aspects is described in detail below.

### Eligibility criteria

The inclusion criteria are ambulatory men or women aged 18–80; Karnofsky score  $\geq 70\%$ ; histologically proven gastric adenocarcinoma on biopsy (including Lauren classification); proven clinical stage of cT2n+M0 or cT3-4a/n+M0 by baseline ultrasound endoscope, enhanced CT/MRI examination or diagnostic laparoscopy using Habermann standards; no past chemotherapy or radiotherapy before diagnosis; tumour located in the middle and lower third of the stomach; achievable naked-eye complete resection (R0/1) via distal subtotal gastrectomy plus D2 lymphadenectomy; haematology and biochemistry index meet the following: haemoglobin  $\geq 80\text{ g/L}$ , absolute neutrophil count  $\geq 1.5 \times 10^9/\text{L}$ , platelet  $\geq 100 \times 10^9/\text{L}$ , Alanine transaminase (ALT) and Aspartate transaminase (AST)  $\leq 2.5$  times the upper limit of normal value, Alkaline phosphatase (ALP)  $\leq 2.5$  times the upper limit of normal value, serum total bilirubin  $< 1.5$  times the upper limit of normal value, serum creatinine  $< 1$  times the upper limit of normal value, and serum albumin  $\geq 30\text{ g/L}$ ; no severe concomitant disease that leads to survival  $< 5$  years; willing and able to comply with the study protocol; and written consent agreement before enrolment and fully aware of the right to quit the study at any time with no loss.

Patients are excluded from the study if they meet one of the following: pregnant or breastfeeding; uncontrolled seizure, central nervous system diseases or mental disorders; history of upper abdominal surgery (except for laparoscopic cholecystectomy); history of gastric surgery (including diagnosis procedure such as endoscopic submucosal dissection and endoscopic mucosal resection); other malignant diseases in 5 years (except for cured skin carcinoma and cervical carcinoma in situ); clinically severe or active heart diseases, such as symptomatic coronary heart disease, the New York Heart Association (NYHA) grade II or above congestive heart failure, severe arrhythmia, or myocardial infarction in 6 months; cerebral haemorrhage or infarction in 6 months; organ transplant recipient under immunosuppressive therapy; severe uncontrolled repeated infection or other severe uncontrolled concomitant diseases; medium or severe renal damage (creatinine clearance rate  $\leq 50\text{ mL/min}$  or serum creatinine greater than the upper limit of normal value); other diseases requiring synchronous surgery; requiring emergent surgery due to oncological emergency (eg, bleeding, perforation, obstruction); forced expiratory volume in 1 s  $< 50\%$  of expected value; and participated in other studies 4 weeks before the randomisation.

**Figure 1** Flow chart.

#### Randomisation and blinding

Patients are enrolled by the oncologists on the team. Eligible patients treated with advanced gastric cancer at the Gastrointestinal Cancer Center of Peking University Cancer Hospital and Institute first receive neoadjuvant chemotherapy with three cycles (3 weeks for one cycle)

of intravenous oxaliplatin (130 mg/m^2 on day 1 of each cycle) plus oral capecitabine (1000 mg/m^2 twice daily on days 1-14 of each cycle). Three weeks after the completion of neoadjuvant chemotherapy, assessment on the resectability of the tumour is conducted on the basis of vital sign examination, physical examination, laboratory

tests, electrocardiograph, lung function examination and tumour evaluation. Patients who passed the resectability confirmation are then randomised to receive either laparoscopic distal gastrectomy with D2 lymph node dissection (group A) or open distal gastrectomy with D2 lymph node dissection (group B) on a 1:1 ratio. Randomisation is achieved using random number table by the data manager and allocation is not concealed. While blinding surgeons or participants is not feasible, pathologists are blinded on the types of surgical approach.

### Treatments

A standard laparoscopic or open distal gastrectomy with D2 lymphadenectomy (including lymph nodes of numbers 1, 3, 4sb, 4d, 5, 6, 7, 8a, 9, 11p and 12a) is performed by two experienced surgeons, according to the Japanese Gastric Cancer Treatment Guidelines 2014 (V.4) and the Japanese Classification of Gastric Carcinoma (3rd English edition).

In the open group, an approximately 20–25 cm incision is made from the falciform process to the periumbilical area. In the laparoscopic group, one 10 mm trocar for the camera is inserted below the umbilicus. Another three 10 mm ports are inserted in the left upper quadrants 2 cm below the left lower rib margins, the right and left flank areas, respectively. One 5 mm trocar is lastly placed on the right upper quadrants 2 cm below the right lower rib margins. Anastomosis is performed using the instrumental method. The specimen was pulled out through a small median incision under the xiphoid (about 6–8 cm).

For those who underwent laparoscopic gastrectomy, the case is required to be converted to open surgery if one of the following happens: confluent lymph nodes with long axis >3 cm, severe or life-threatening intraoperative complications such as intra-abdominal massive haemorrhage, severe organ damage, or other technical or instrumental factors that require conversion to open surgery.

All patients are managed by a standardised clinical pathway after the surgery. Discharge is recommended when the patients have tolerated more than 2 days of soft diet without abdominal pain or fever. All patients start to accept five cycles of oxaliplatin and capecitabine regimens for postoperative adjuvant chemotherapy within 6 weeks postsurgery. Dose reductions or interruptions are allowed to manage potentially serious or life-threatening adverse events (AEs). In cases of oxaliplatin-related neurological AEs, capecitabine can be continued as monotherapy. Oxaliplatin monotherapy is not allowed. Palliative and supportive care are offered as needed for disease-related symptoms.

### Outcomes

The primary endpoint is 3-year recurrence-free survival (RFS) rate. Recurrence includes any recurrence (local or regional, or distant) and death due to any cause (both gastric cancer and non-gastric cancer causes of death). The secondary endpoints are overall survival, radicalness of surgery, 30-day postoperative surgical morbidity and mortality, 2-week postoperative recovery index, cycles of

postoperative chemotherapy, and up to 1-year postoperative quality of life. The radicalness of surgery includes assessments on the number of lymph nodes retrieved and the length of resection margin. Postoperative complications are defined as complications occurring within 30 days after surgery, and will be classified according to the Clavien-Dindo classification system. Hospital mortality is defined as death occurring within 30 days after initial surgery, regardless of the cause. Postoperative recovery index considers blood loss, first aerofluxus time, first defaecating time, first time on a liquid diet, time of pulling gastric tube and drainage, and length of hospital stay. Postoperative pain intensity is measured by using a Visual Analogue Scale up to 72 hours after surgery. The time of applying intravenous patient-controlled analgesia and rescue morphine consumption is recorded. One-year postoperative quality of life is assessed using the European Organisation for Research and Treatment of Cancer (EORTC) Quality of Life questionnaires (QLQ-C30 and EORTC-QLQ-STO22).

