## Data collection and analysis

Trained oncologists collect data via datasheets on paper daily until the patient's discharge. Initial staging and therapeutic efficiency assessment include endoscopy, endoscopic ultrasound, non-contrast-enhanced CT scan of the thorax, and contrast-enhanced CT scan of the abdomen and pelvis. MRI examination will be used as an alternative to CT scan if the patient is allergic to radiocontrast agent or has other contraindications on CT examination. Laparoscopy and peritoneal washings for malignant cells are conducted before and after neoadjuvant chemotherapy. Tumour response evaluation after neoadjuvant chemotherapy includes both imageological and pathological examinations. The former is conducted according to the Response Evaluation Criteria in Solid Tumours (V.1.1). The latter is performed in accordance with the Tumour Regression Grade Standards of the National Comprehensive Cancer Network clinical practice guidelines in oncology for gastric cancer (V.3.2015). Gastrectomy specimens are open along the greater curvature, and macroscopic examination is conducted before representative blocks are taken from the tumour and its surrounding areas, and paraffin-embedded. All removed lymph nodes are embedded separately. Microscopic features are reported according to the seventh edition of the International Union Against Cancer TNM classification.

Information on prognostic status is collected via follow-up up to 3 years after the last treatment. Follow-up is conducted on a 3-month basis in the first 2 years and every half year in the third year. To promote participant retention and complete follow-up, three attempts are made to contact and remind the participants to come to the hospital for follow-up, and their transportation fees are covered by the research project. Every follow-up, participants receive physical examinations (ie, height, weight, Karnofsky score and others), laboratory tests (including blood cell test, blood biochemical test and serum tumour marker test) and imageological examinations (including ultrasonography, enhanced CT/MRI, endoscopy and chest radiograph). Tumour assessment will be conducted if recurrence is suspected, and further treatments such as surgery or chemotherapy will be performed when needed and will be recorded on the CRF. Data entry in EpiData is completed by two independent staff, with a third staff monitoring the quality.

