Intention-to-treat and per-protocol approach will be used for efficacy analysis. As-treated analysis will be applied for safety analysis. For variables with a significant amount of missingness, multiple imputations will be conducted for the purpose of sensitivity analysis. In terms of descriptive analysis, categorical data will be presented as number and percentage. Continuous variable will be presented as mean and SD if normally distributed, or as median and range otherwise. The primary analysis in this study aims to compare the 3-year RFS rate between laparoscopic and open gastrectomy after neoadjuvant chemotherapy. The date of recurrence is defined as the date of all-cause death or when a clinician judges recurrence

considering all information including serum tumour and the results of imageological examination. The RFS curves will be constructed as time-to-event plots using the Kaplan-Meier method. Log-rank tests will be used to make a simple comparison of the survival curves. Cox proportional hazards model will be performed to compare RFS after taking into account potential confounders. The overall survival will also be analysed in the same manner. Subgroup analyses will be conducted by age group, tumour location, body mass index category and TNM stage. All statistical analyses will be conducted in standard statistical software with a significance level of 0.05.

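### The RFS event rule lists only recurrence and death, so a randomised patient never cleared of disease has no event at surgery

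*Protocol*

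**What the plan says.** All references are to the Protocol.

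- **Endpoint (Outcomes).** "The primary endpoint is 3-year recurrence-free survival (RFS) rate". The events are set out as: "Recurrence includes any recurrence (local or regional, or distant) and death due to any cause".
- **Dating (Data collection and analysis).** "The date of recurrence is defined as the date of all-cause death or when a clinician judges recurrence", the judgement resting on all available information, including markers and imaging.
- **Order of events (Randomisation and blinding).** Allocation follows the resectability check after chemotherapy and comes before the operation. Surgeons and participants are not blinded; pathologists are.
- **Analysis sets (Data collection and analysis).** "Intention-to-treat and per-protocol approach will be used for efficacy analysis".
- **Entry (Eligibility criteria).** Patients need "achievable naked-eye complete resection (R0/1) via distal subtotal gastrectomy plus D2 lymphadenectomy". This is an expectation at entry, not a surgical result.
- **Surgical quality (Outcomes).** "The radicalness of surgery includes assessments on the number of lymph nodes retrieved and the length of resection margin". Neither R status nor the R0 rate is named.
- **Staging (Data collection and analysis).** "Laparoscopy and peritoneal washings for malignant cells are conducted before and after neoadjuvant chemotherapy". The assessments listed before randomisation end with a general tumour evaluation and do not say whether this laparoscopy is part of it.

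**The concern.** Recurrence presupposes that disease was first cleared. A patient whose resection was abandoned, was R2, or revealed M1 disease was never recurrence-free, yet stays in the intention-to-treat set because allocation came before surgery. Neither the event list nor the dating rule has an entry for such a patient. Two events remain possible: death, or the day a clinician decides to call existing disease a recurrence. The first comes late. The second has no fixed trigger and is made in an open-label trial, so its timing could differ between arms.

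Incomplete clearance is the failure most directly tied to surgical approach. If it were more frequent after laparoscopy, late or missed events would make the laparoscopic arm look better than it is, and the non-inferiority conclusion would be easier to reach.

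**Working it through.** **1. Does any stated rule cover these patients?** The event list gives recurrence and all-cause death. The dating rule gives the date of death or of a clinician's judgement. The Treatments section covers conversion to open surgery but not an abandoned or incomplete resection. No rule covers them, and intention to treat keeps them in the analysis. That such a patient starts event-free is therefore an inference from the definition plus the analysis set; the Protocol does not say so, and it states no time origin for RFS.

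**2. Effect on the 3-year rate, by hand.** The Protocol gives 48 per arm. The other inputs are assumptions: *k* patients with residual disease, all in the laparoscopic arm and none in the open arm, whose only later event is death, exponential with a median of 1 year.

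- Chance that such a patient is alive, and so event-free, at 3 years: 0.5³ = 0.125.
- Rise in the arm's event rate if each counts as an event at surgery: *k* × 0.125 / 48.
- *k* = 1: 0.26 points. *k* = 2: 0.52. *k* = 3: 0.78. *k* = 4: 1.04.

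**3. Effect on the HR, by simulation.** The inputs are those of step 2, with exponential RFS and 3-year RFS of 50, 60 or 70% for all other patients in both arms (assumed). There were 300 simulated trials per scenario, with follow-up cut at 3 years and a Cox HR. Each simulated data set was analysed twice: as written (event at death) and with the event at time zero. Each cell shows the mean HR as written, then with the event at surgery, and the shift in brackets.

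| *k* | 3-year RFS 50% | 60% | 70% |
|---|---|---|---|
| 1 | 1.042 → 1.060 (0.018) | 1.049 → 1.066 (0.017) | 1.023 → 1.043 (0.020) |
| 2 | 1.078 → 1.112 (0.034) | 1.087 → 1.124 (0.037) | 1.140 → 1.183 (0.043) |
| 3 | 1.119 → 1.172 (0.053) | 1.080 → 1.137 (0.057) | 1.134 → 1.189 (0.055) |
| 4 | 1.128 → 1.200 (0.072) | 1.152 → 1.235 (0.083) | 1.223 → 1.307 (0.084) |

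The simulated 3-year RFS difference moved by 0.2 to 1.1 points over the same scenarios, in line with step 2. The absolute HRs carry simulation noise of a few hundredths (with *k* = 0 they were 0.972, 0.988 and 1.020). The shifts are paired and much steadier.

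**4. Against the Protocol's criterion.** The first criterion in Sample size is an HR estimate below 1.12, which leaves 1.12 − 1.00 = 0.12 above equality. A shift of 0.03 to 0.04 for two patients is 0.03/0.12 = 25% to 0.04/0.12 = 33% of that room.

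The Protocol states no figure for this point, so there is none of its own to reproduce.

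**The case against.** The case for leaving the text alone has real substance.

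- **These patients are not event-free for good.** Death counts, and clinicians may judge recurrence at visits every 3 months for the first 2 years, with imaging. If persisting disease is labelled early, the delay is short. This stands, and it is why the effect on the 3-year rate is small.
- **A reader might infer a loss of 2/48 = 4.2 points for two patients, about half of the 8% the Protocol treats as critical.** That requires that they never have an event within 3 years. Nothing in the Protocol says so, and step 2 of the working gives about 0.5 point.
- **A reader might infer that the per-protocol analysis would delete them.** The Protocol does not define that set, and a patient with an R2 resection did undergo the allocated gastrectomy. The point is conjecture.
- **A reader might infer a bias towards laparoscopy as a fact.** The direction depends on an imbalance for which the Protocol gives no figures. M1 disease found at operation was there beforehand and is balanced in expectation.
- **A reader might infer that M1 disease surfaces only after allocation.** The general tumour evaluation before randomisation can include the post-chemotherapy laparoscopy; its not being named there is weak evidence. Entry criteria and the resectability check also make such cases fewer.
- **The surgical-quality endpoint is not worded as an exclusive list.** Margin length is assessed and overall survival is a secondary endpoint, so it would be too strong to call the trial blind to incomplete clearance.
- **Special-case coding often sits in an SAP.** Here, though, the Protocol itself fixes the event list and dating rule for the primary endpoint, and as fixed they do not fit the randomised population.

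These objections limit the size of the problem. They do not supply the missing rule.

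**Conclusion.** The concern holds as a defect of definition with a modest likely effect. The primary event rule suits patients cleared of disease, while the analysis population is everyone randomised before surgery. For those never cleared, the event is delayed to death or to an unblinded judgement with no fixed trigger, and may be missed.

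Under the stated assumptions, one to four cases move the 3-year RFS difference by about 0.2 to 1 point, and two cases move the HR by about 0.03 to 0.04. The HR shift matters more, because the first non-inferiority criterion is an HR point estimate. Placing every case in the laparoscopic arm and allowing death as the only later event both enlarge the shift, so earlier labelling or a more even split would make it smaller. Case frequency, 3-year RFS and time to death are assumptions. The change is worth making, but the gap does not by itself undermine the trial.

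**What to change.** 1. In the intention-to-treat RFS analysis, count no resection, R2 resection or M1 disease found at surgery as an event on the day of surgery, identically in both arms.
2. Count R1 resection the same way in a sensitivity analysis.
3. Add the R0 rate to the surgical-quality endpoint, with margin status taken from the existing blinded pathology reports.
4. Reconcile Randomisation and blinding with Data collection and analysis on whether the post-chemotherapy laparoscopy and washings belong to the tumour evaluation done before randomisation. Only the text needs reconciling; no change to the timing of the procedure is proposed, and the Abstract says that 96 patients have already been enrolled.

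The cost is wording in the endpoint definition and one extra tabulation, with no new patients or procedures. The downside is slightly lower RFS in both arms, including some events (M1 found at operation) that have nothing to do with the surgical approach. The new rule should be dated and adopted before RFS is compared by arm.
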